## 7. DETAILS ON STUDY PROCEDURES

Please also refer to the Study Calendar in [Section 6](#).

### 7.1 Registration procedures

- Informed consent
- Buccal swab collection should be performed no later than one week prior to the Baseline study visit

### 7.2 Baseline Procedures

Baseline study visit should be completed no earlier than 2 weeks and no later than 8 weeks from the first ESAS completion during the clinic visits or utilizing virtual care.

- Subject demographics: Race, Ethnicity, Work Status, Insurance Status, Zip code
- Medical history: data related to disease and/or diagnosis, including cancer type, stage of disease, and ECOG performance status
- Treatment history: therapeutic interventions including surgery within 30 days of Baseline, active chemotherapy, active radiation, and active supportive care therapy
- Drug allergies to medications listed in [Appendix D](#)
- ESAS [Appendix A](#) collected as a SOC
- PHQ9 [Appendix B](#) collected preferably electronically within 2 business days prior to the study visit, or alternatively on paper during the clinic visit or by phone call within 2 business days prior to the study visit
- Medications listed in [Appendix D](#), currently taken at the time of Baseline study visit and/or newly prescribed during the visit and, other drugs and/or drug modifications recommended by the pharmacist or provider based on PGx test results outside those in [Appendix D](#)
- Use of PGx to guide/modify pharmacotherapy regimen
- HCRU

### 7.3 Study Visits

- A total of 3 subsequent study visits will occur every 4 weeks ( $\pm$  1 week) after the Baseline visit.
- During *each* study visit (in a clinic or virtually), the following information will be collected:
  - Drug allergies to medications listed in [Appendix D](#)
  - ESAS [Appendix A](#) collected as a SOC
  - PHQ9 [Appendix B](#) collected preferably electronically within 2 business days prior to the study visit, or alternatively on paper during the clinic visit or by phone call within 2 business days prior to the study visit
  - Addition or change in medications listed in [Appendix D](#), and/or dosages, and other drugs and/or drug modifications recommended by the pharmacist or provider based on PGx test results outside those in [Appendix D](#)
  - Use of PGx to guide/modify pharmacotherapy regimen
  - HCRU

## 7.4 Final Visit

- The Final study visit will occur 4 weeks ( $\pm$  1 week) after the third completed Study Visit.
  - Drug allergies to medications listed in [Appendix D](#)
  - ESAS [Appendix A](#) collected as a SOC
  - PHQ9 [Appendix B](#) collected preferably electronically within 2 business days prior to the study visit, alternatively via paper during a clinic visit or by phone call within 2 business days prior to the study visit
  - Addition or change in medications listed in [Appendix D](#) and/or dosages, and other drugs and/or drug modifications recommended by the pharmacist or provider based on PGx test results outside those in [Appendix D](#)
  - Use of PGx to guide/modify pharmacotherapy regimen
  - HCRU
  - Patient survey ([Appendix C](#))
  - Subject demographics (part of the final survey): annual household income and education level.

## 7.5 Correlative Study Procedures

Correlative specimens for this study include buccal swabs for DNA extraction and genotyping for germline pharmacogenes to be analyzed per [Section 5.1](#). After obtaining informed consent, two buccal swabs will be collected by the research designee. No processing of samples is required prior to transfer. The samples will be transferred to the Levine Cancer Institute Molecular Biology Laboratory for DNA extraction and genotyping.

### 7.5.1 Source and Timing of Biospecimen Collections

All buccal specimens will be obtained after informed consent no later than one week before the Baseline study visit. The specimen may be obtained the same day as informed consent. The research designee will instruct the subject on the appropriate buccal swab collection.

Either the research staff member or the subject can perform the swabbing, depending on subject preference. Subjects will be given the option to collect buccal swabs at home, in which case a buccal collection kit with instructions on collection and shipping will be mailed to the subject. Subjects will be asked to collect buccal swabs and ship within 48 hours, ideally (max 96 hours) of receiving the buccal swab kit.

All samples collected on site will be transported by either research or laboratory staff at ambient temperature to the Molecular Biology Laboratory at the Levine Cancer Institute. Samples collected by the subject at home will be mailed at ambient temperature directly to the Molecular Biology Laboratory. Samples will be logged in and processed for DNA extraction and genotyping per laboratory procedures.

### 7.5.2 Storage of Biospecimens

Specimens will be stored in the Molecular Biology Laboratory only until the pharmacogenomic results have been confirmed by both the Laboratory Director and Sponsor-Investigator (approximately one week from sample receipt). Once PGx results are confirmed by the Laboratory Director and Sponsor-Investigator, all samples will be discarded according to laboratory procedures.

## **8. REMOVAL OF SUBJECTS FROM STUDY**

### **8.1 Off Study**

Subjects are considered Off Study after completion of the subject survey and the Final visit that occurs 4 weeks ( $\pm$  1 week) after the third completed Study Visit.

Subjects may stop their participation in this study at any time if they no longer wish to participate or if the Investigator believes this to be in the best interest of the subject. When subjects are removed from the study, the reason for study removal and the date the subject was removed should be documented. Other reasons a subject may be removed from study include, but are not limited to:

- Subject non-compliance with study participation, in the opinion of the Investigator
- The subject or legal representative withdraws study consent
- The subject's tumor is confirmed to be a benign per provider
- Buccal swab collected and shipped more than 96 hours after receiving the buccal swab kit or if otherwise deemed non-viable
- The subject unwilling to recollect the buccal swabs if DNA from the first buccal swabs is not viable
- The subject is lost to follow-up
- Investigator's decision to withdraw the subject
- Subject death

Subjects that are Off Study will not participate in any study- related procedures, including data collection.

## **9. DATA AND SAFETY MONITORING PLANS**

Data will be collected in electronic case report forms (eCRFs). The database uses fully validated secure web-enabled software that conforms with 21CFR Part 11 requirements. Study personnel will be trained on data entry by the sponsor and provided protocol-specific eCRF guidelines.

This protocol will be monitored according to the processes in effect for all LCI investigator-initiated studies, the protocol-specific monitoring plan and will abide by applicable regulations and guidelines (e.g. Good Clinical Practice [GCP]). The Sponsor-Investigator and other sponsor-level team members will meet regularly to monitor subject consents, enrollment and retention, safety data, and timeliness/validity/integrity of the data. Documentation of these meetings will be kept with study records. The Sponsor-Investigator will submit reports to the

LCI Data and Safety Monitoring Committee according to the institutional Data and Safety Monitoring Plan.

This study will be monitored to ensure the study is conducted in compliance with the study protocol, SOPs of the LCI and Atrium Health Office of Clinical and Translational Research (and/or other participating institutional SOPs), the FDA, and other applicable regulations and guidelines (e.g. GCP).

Investigators and/or their delegated study personnel will be required to be available during the monitoring visits.

## **10. POTENTIAL RISKS/UNANTICIPATED PROBLEMS**

### **10.1 Potential Risks**

There is no investigational treatment as part of this clinical trial. All supportive care treatments are considered standard of care. The primary intervention is PGx testing. The potential risks are limited to those associated with subject confidentiality, specimen collection, and knowledge of PGx test results. Nonetheless, the American College of Medical Genetics has deemed PGx testing as low risk since these genes are not related to disease susceptibility or prognosis.

#### **10.1.1 Subject Confidentiality**

All data and records generated during this study will be kept confidential in accordance with Institutional policies on subject privacy and HIPAA and that the investigator and other site personnel will not use such data and records for any purpose other than conducting the study. We do not anticipate any breach of confidentiality as no records will be shared with any personnel outside the research team. All medical information, including assessments and other medical records will be recorded and stored in a database. The databases will exist on a password protected secured server. Medical records data will be abstracted by the Research Designee. All records will be kept confidential.

Pharmacogenomic test results will be added to each subjects' Electronic Medical Record. Subjects will be provided a copy of his/her pharmacogenomic test results at their request, which can be used for other clinical/medication decisions downstream. The subject is free to share this information with anyone.

#### **10.1.2 Biomarker Specimen Collection**

##### **Buccal Swabs**

No adverse events are expected for buccal swab procedures. If a subject has an unexpected adverse event, the Investigator will treat the subject according to standard of care practices until the adverse event resolves.

Adverse events will not be recorded for the purposes of this study but will be a part of the subject's medical record as per standard operation procedures.

### **10.1.3 Emotional Distress**

Some questions in the questionnaires could create emotional distress or confusion. If a subject experiences distress or confusion, the questionnaire process will be interrupted or discontinued, and the Research Designee will follow-up with the Sponsor-Investigator. Knowledge of PGx test results may result in emotional distress; however, the American College of Medical Genetics have identified pharmacogenes as "low risk" as they are not related to hereditary disease conditions, but rather how a person may metabolize or process various medications. There is a low likelihood of emotional distress caused by knowledge of PGx information. All subjects will be counseled on their test results by a trained pharmacist.

## **10.2 Unanticipated Problems (UAP)**

### **10.2.1 Definition**

A UAP is any incidence, experience or outcome that is unexpected (e.g., a lost or stolen laptop computer that contains sensitive study information) given the information provided in research-related documentation (e.g., informed consent) and the study population characteristics, that is related or possibly related to participation in the research study and places the participant at an increased risk.

### **10.2.2 Reporting**

All UAPs occurring during the conduct of a protocol and meeting the definition of a UAP will be reported to the IRB per IRB reporting requirements.

## **11. STATISTICAL CONSIDERATIONS**

### **11.1 Milestones**

Registration Date: Date of consent

Enrollment Date: Date the buccal swab is collected.

Off Study: Date of the Final visit that occurs 4 weeks ( $\pm$  1 week) after the third completed Study Visit.

## **11.2 Sample Size and Accrual**

Enrollment to the study will continue until 65 evaluable subjects have been identified ([Section 11.3](#)).

We anticipate enrolling 80 eligible subjects, of which we estimate 65 will be evaluable (defined in [11.3](#)). With this sample size, the width of the 95% Clopper-Pearson confidence interval will be  $\leq 25\%$ , regardless of the observed DDSM rate.

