KEY INCLUSION CRITERIA	
 
• Adult cancer patients <math>\geq 18</math> years of age who have had either an initial visit in the Department of Supportive Oncology’s palliative medicine clinic or a re-establishment of care visit with the last visit being at least 1 year prior, able and willing to sign the informed consent and provide a buccal sample for PGx testing.
 
• Hematologic malignancy or any stage solid tumor malignancy. Presenting with pain score <math>\geq 4/10</math> and/or depression score <math>\geq 3/10</math> on ESAS (or patients diagnosed with depression with a clinical need to adjust depression medications)
 

STATISTICAL CONSIDERATIONS	
The evaluable population for the primary objective is defined as enrolled subjects with confirmed malignancy (per provider documentation) completing an on-study visit with PGx results available. We anticipate enrolling 80 eligible subjects, of which we estimate 65 will be evaluable.

	With this sample size, the width of the 95% Clopper-Pearson confidence interval will be $\leq 25\%$ , regardless of the observed DDSM rate.
NUMBER OF SUBJECTS	80, to achieve 65 evaluable subjects

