### 3. SUBJECT SELECTION

#### 3.1 Subject Identification and Recruitment

Accrual is expected to be 80 eligible subjects. All patients will complete ESAS during a regularly scheduled visit to the Department of Supportive Oncology's palliative medicine clinic (Palliative medicine clinic). Potential candidates will be identified by reviewing the EMR to identify patients with ESAS pain  $\geq 4/10$  and/or depression  $\geq 3/10$  (or diagnosed with depression with a clinical need to adjust depression medications).

It is expected that 80 eligible subjects will be required to enroll 65 evaluable subjects. In the event that more subjects are required to achieve 65 evaluable subjects, subject enrollment will continue until 65 evaluable subjects have been enrolled.

Target accrual period of this study will be approximately 30 months.

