### **11.4.4 Primary Analysis**

The proportion (the denominator being the number of evaluable subjects) of evaluable subjects undergoing PGx testing and receiving at least one drug/dose selection/modification based on their test results at any study visit where PGx results are available will be calculated, alongside 95% Clopper-Pearson confidence intervals.

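### With 65 evaluable subjects the 95% Clopper-Pearson width can reach 25.3%, so the stated bound of 25% for every observed rate is not correct

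*Combined protocol and SAP*

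**What the plan says.** The primary objective is to estimate the proportion of tested subjects who have at least one drug or dose selection or modification based on their pharmacogenomic results (the DDSM rate). Section 11.2 plans for this as follows: "We anticipate enrolling 80 eligible subjects, of which we estimate 65 will be evaluable". It then states the precision: "With this sample size, the width of the 95% Clopper-Pearson confidence interval will be" no more than 25%, and the Synopsis gives the same bound with the same qualifier, "regardless of the observed DDSM rate".

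Recruitment is tied to the evaluable count. Section 3.1 says that "subject enrollment will continue until 65 evaluable subjects have been enrolled", and Section 11.2 agrees: "Enrollment to the study will continue until 65 evaluable subjects have been identified".

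Section 11.4.4 fixes the analysis. The proportion is calculated with "the denominator being the number of evaluable subjects" and reported "alongside 95% Clopper-Pearson confidence intervals". The plan has no other precision or power calculation, no hypothesis test for the primary endpoint, and no assumed DDSM rate.

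**The concern.** The sentence promises a bound for every possible result, so one outcome with a wider interval makes it wrong. Clopper-Pearson intervals are conservative and are widest when the observed rate is near one half. A bound that is only just met by an approximate method at that point can therefore fail with the exact one.

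The primary aim is estimation, so precision is the design criterion, and this is the only place where the plan quantifies it. With no expected rate stated, the middle of the range cannot be set aside as unlikely. If the result fell there, the published interval would be wider than the protocol said it could be.

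**Working it through.** **Inputs.** n = 65 evaluable subjects (Sections 3.1 and 11.2); two-sided 95% Clopper-Pearson interval (Sections 11.2 and 11.4.4); denominator = evaluable subjects (Section 11.4.4); stated bound = 25% full width for any observed rate (Section 11.2 and Synopsis).

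**Formula.** For x events in n subjects:

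- lower limit = 0.025 quantile of Beta(x, n − x + 1), or 0 if x = 0
- upper limit = 0.975 quantile of Beta(x + 1, n − x), or 1 if x = n
- width = upper − lower

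**Step 1: try to reproduce the plan's figure.** The width was computed for every x from 0 to 65. Widths are symmetric about one half. The counts around the crossing and the maximum are:

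| x | Observed rate | 95% limits | Width |
|---|---|---|---|
| 27 | 41.5% | 29.44% to 54.44% | 24.997% |
| 28 | 43.1% | 30.85% to 55.96% | 25.11% |
| 30 | 46.2% | 33.70% to 58.97% | 25.27% |
| 32 | 49.2% | 36.60% to 61.93% | 25.33% |
| 33 | 50.8% | 38.07% to 63.40% | 25.33% |
| 35 | 53.8% | 41.03% to 66.30% | 25.27% |
| 37 | 56.9% | 44.04% to 69.15% | 25.11% |
| 38 | 58.5% | 45.56% to 70.56% | 24.997% |

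The stated maximum of 25% is not reproduced. The actual maximum is 25.33%, an excess of 25.33 − 25 = 0.33 percentage points. The width exceeds 25% at exactly ten counts, x = 28 to 37, and at no others. Inverting the exact binomial tail by bisection gave the same limits at x = 26, 27, 28, 32, 33, 37, 38 and 39.

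**Step 2: find the n that would meet the bound.** The maximum width over all x is:

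| n | Maximum width |
|---|---|
| 64 | 25.54% |
| 65 | 25.33% |
| 66 | 25.14% |
| 67 | 24.94% |

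The smallest n that keeps every outcome at or below 25% is 67. At the plan's own evaluable fraction, 65/80 = 0.8125, that would mean enrolling 67/0.8125 = 82.5, or about 83 subjects.

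**Step 3: check whether another reading gives 25%.** At n = 65 the maximum widths by other methods are Wald 24.31%, Jeffreys 23.86%, Wilson 23.62%, Agresti-Coull 23.62% and 90% Clopper-Pearson 21.60%. A 95% Clopper-Pearson interval with all 80 enrolled subjects gives at most 22.79%. All of these are below 25%, but none is the interval and denominator that the plan names.

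**Step 4: ask how likely the excess is.** The plan gives no expected rate, so the true rate is an assumption here. The binomial probability that the count falls in 28 to 37 is:

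| Assumed true rate | Probability |
|---|---|
| 20% | below 0.01% |
| 30% or 70% | about 2% |
| 40% or 60% | 35% |
| 45% or 55% | 65% |
| 50% | 79% |

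**The case against.** The strongest reply is that this is rounding. The bound is given as a whole percentage, and 65 is the smallest n whose worst-case width rounds to 25% (25.33%, against 25.54% at n = 64, which rounds to 26%). On that view the calculation was sound and only the inequality sign is misplaced. The plan does not say how 65 was chosen, so this is inference, but it fits the figures.

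Nor does any decision depend on the bound. There is no null rate, test or success threshold, and the reported interval will be correct whatever the planning sentence says. The worst excess is 0.33 points of full width, roughly 0.17 points on each side. The plan also describes the precision at 65 without saying that 65 was derived from a 25% requirement.

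All of this stands as an argument about size, and it makes the point a minor one. It does not make the sentence true: an upper bound asserted for every rate fails at ten of the 66 possible outcomes.

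**Conclusion.** The statement is wrong as written, by a small amount. At 65 evaluable subjects the width reaches 25.33% and exceeds 25% for observed rates from 43.1% to 56.9%. A guarantee for every rate needs 67 evaluable subjects. This rests only on the interval method, confidence level and denominator that the plan itself specifies; no assumption about the true rate is needed. That rate affects only how likely the excess is to appear in the result. The design, the primary analysis and its validity are unaffected. It is worth correcting because it is the plan's only precision justification and is easily checked.

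**What to change.** Keep 65 evaluable subjects. In Section 11.2 and in the Synopsis, replace the bound with a true one: the width of the 95% Clopper-Pearson interval will be at most 25.4%, and at most 25% when the observed DDSM rate is below 43% or above 57%. A shorter statement of at most 25.4% would also do.

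The cost is one sentence in two places and a slightly less favourable stated precision. Enrolment, conduct and analysis do not change. If the sponsor prefers to keep the 25% guarantee, the evaluable target must rise to 67 (about 83 enrolled at the planned evaluable fraction) wherever 65 and 80 appear. A gain of 0.33 points hardly warrants that.

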## **11.3 Analysis Populations**

Analyses of the primary objectives and secondary objectives concerning counts of PGx-guided drug/dose selections or modifications based on their test results will be conducted on the evaluable population, defined as the population of enrolled subjects with confirmed malignancy (per provider documentation) and completing at least one study visit where PGx results are available (including the baseline visit).

Analyses of secondary objectives concerning the impact of PGx on pain and depression scores will be conducted on the primary evaluable population with valid pain and/or depression scores for at least one post-Baseline Study visit.

Analyses of secondary objectives concerning health care utilizations, costs, and subject survey responses and all exploratory objectives will be conducted on all enrolled subjects.

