### 2.2.2 Secondary Endpoints

- A count variable will be recorded for each subject undergoing PGx testing indicating the total number of drug/dose selections or modifications received across all study visits where PGx results were available.
- Pain scores assessed by the ESAS and depression scores using PHQ9 will be recorded for each subject at the Baseline and all the visits.
- Health care resource utilization (HCRU) and costs will be estimated based on the number of inpatient, emergency department, outpatient, and pharmacy encounters, among others, occurring one year prior to and during the study period.
- Discrete variables will be recorded to indicate subject survey responses.

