### 5.1.3 Subject Survey ([Appendix C](#))

The patient survey is intended to assess the subject's perspective of pharmacogenomics testing. The survey will be administered preferably electronically, alternatively over the phone or on paper during a clinic visit at the Final visit time-point or sooner if withdrawn.

If data from ESAS, PHQ9 questionnaires, and Subject survey are missing, when possible, the reason for the missing data will be categorized and documented as follows:

- the subject felt too ill;
- clinician or nurse felt the subject was too ill;
- the subject felt it was inconvenient or took too much time;
- the subject felt it was a violation of privacy;
- the subject didn't understand the actual language or was illiterate;
- administrative failure to distribute the questionnaire;
- other, specify;
- unknown.

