Research team will collect PHQ9 prior to the study visit, preferably electronically or by phone, within 2 business days and send them to the Supportive Oncology provider and Sponsor-Investigator. If the response for the PHQ9 question #9 is anything greater than 0, a research designee will contact the applicable LCI social worker. Alternatively, PHQ9 can be collected during clinic visits on paper.

ESAS will be obtained during a clinic visit or utilizing virtual care.

ESAS score done historically visit per standard of care at the initial palliative medicine visit will be collected in the dataset and used for analysis ([Section 11.4.5](#))

Medications listed in [Appendix D](#), currently taken and/or newly prescribed during the visit, and other drugs and/or drug modifications recommended by the pharmacist or provider based on PGx test results outside those in [Appendix D](#) list will be collected every study visit.

Use of PGx test results should be documented any time a drug/dose modification is made (during palliative medicine visits or in between visits).

HCRU (defined as any encounter classified as an outpatient (OP), inpatient (IP), or emergency department (ED) encounter) occurring during the study period will be collected by a research designee. Each encounter will be counted as unique per classification. IP encounters that result from an emergency department presentation will be classified as both an ED encounter and IP encounter. Any encounter lasting longer than 24 hours will be considered an IP encounter. Insurance status and/or type and reason for presentation at each encounter will also be collected.

Survey will be preferably administered electronically (distributed to the subject's email within 30 days after the Final visit). Alternatively, a research designee can collect a survey via paper during the Final visit at the clinic (or sooner if withdrawn) or over the phone as an option.

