### 11.4.5 Secondary Analysis

Total counts and descriptive statistics of the number of drug/dose selection/modifications made due to subject PGx test results at all visits where PGx results are available will be summarized.

A single-arm analysis for the PGx cohort will be performed: Descriptive statistics of ESAS pain scores and PHQ-9 depression scores will be calculated and summarized at study visits. Repeated-measures linear mixed models will be estimated for pain and depression, separately, adjusted for baseline clinicodemographic characteristics and include a main effect for time and a random effect for subject.

The following analysis will be performed for both the PGx and control cohorts:

A matched analysis for ESAS pain and depression scores will be carried out, comparing the study cohort to a matched cohort of unique patients receiving clinical management alone during the same time period the trial is enrolling. Standard-of-care patients with ESAS pain  $\geq 4$  and/or depression scores  $\geq 3$  at their first visit to the palliative medicine clinic or a re-establishment of care visit with the last visit being at least 1 year prior—these visits occurring within the same time period the trial is enrolling—will be identified and considered in the matched analysis.

Enrolled subjects will be matched to a similar case in cohort by:

- ESAS pain and depression symptom scores at first visit to palliative medicine clinic (i.e., study screening for study cohort)
- Age
- Sex
- Race
- Clinic visit schedule.

Between-group comparisons of those study subjects and control patients will be performed estimating repeated-measures linear mixed models for pain and depression, separately, to estimate the effect of PGx testing (i.e., treatment effect) on symptom scores adjusted for baseline clinicodemographic characteristics, a main effect for treatment, for time, an effect for treatment by time interaction, and a random effect for subject.

Additionally, the average post-baseline symptom score will be calculated for each individual (separately for pain and depression). The distributions of the average post-baseline symptom scores will be compared between the cohorts using analysis of variance techniques with adjustments for clinicodemographic characteristics.

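### Section 11.3 drops evaluable PGx subjects with no post-Baseline score from the pain and depression mixed models; if Baseline is an outcome row and loss depends on the Baseline score, the estimated change is biased toward zero

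*Combined protocol and SAP*

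**What the plan says.** Section 11.3 sets two populations that matter here. The evaluable population for the primary endpoint requires a confirmed malignancy and "completing at least one study visit where PGx results are available (including the baseline visit"). The pain and depression analyses then use only the "primary evaluable population with valid pain and/or depression scores for at least one post-Baseline Study visit". A subject with Baseline data alone meets the first definition and fails the second.

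That subject's scores are held. Section 2.2.2 states: "Pain scores assessed by the ESAS and depression scores using PHQ9 will be recorded for each subject at the Baseline and all the visits". Table 2 (Section 6.1, footnote 10) adds that the ESAS from the initial palliative visit "will be collected in the dataset and used for analysis".

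On the model, Section 11.4.5 says: "Repeated-measures linear mixed models will be estimated for pain and depression, separately, adjusted for baseline clinicodemographic characteristics". For the single-arm analysis the models "include a main effect for time and a random effect for subject". The text does not say whether the Baseline symptom score is a response or a covariate. It states no missing-data assumption for these models. The only sensitivity analyses in 11.4.5 belong to the utilization and cost paragraph.

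**The concern.** A likelihood-based mixed model can use partial records. If Baseline is among the outcome rows, a subject with a Baseline score and nothing later still informs the Baseline mean and, through the within-subject correlation, the later means. The estimates then remain valid when loss depends on scores already observed. Removing such subjects beforehand gives up that protection.

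Loss related to symptoms is plausible in this population. Subjects enter because of pain and/or depression, Section 3.4 lists death and inability to complete visits among the withdrawal reasons, and Section 5.1.3 codes reasons for a missing questionnaire such as "clinician or nurse felt the subject was too ill". Section 8.1 ends data collection once a subject is off study.

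At stake is the single-arm part of the first secondary objective, the impact of PGx on pain and depression. If those lost had worse Baseline scores, the remaining subjects start lower. Their later mean is then too low for the cohort as a whole, and their fall from Baseline is too small. The primary proportion is not affected.

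**Working it through.** **No figure in the plan to reproduce.** The plan's only sample-size figure is the width of the confidence interval for the primary proportion, which does not enter here. The drop from 80 enrolled to 65 evaluable (15/80) occurs before a subject becomes evaluable, so it is not a post-Baseline attrition rate. Section 5.1.1 gives four post-Baseline visits (three study visits and the Final visit).

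**Assumed inputs.** 65 subjects; Baseline pain mean 5, SD 2.5; true change -1.0; constant within-subject correlation ρ = 0.4 or 0.6; a fraction p = 10%, 20% or 30% (about 7 to 20 of 65) lost before any post-Baseline score; logistic loss rising with Baseline pain, slope 0.2 or 0.4 per point.

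**Formula.** Let g be the Baseline mean of those lost minus that of those retained. The retained subjects' Baseline mean is too low by δ = p × g. With loss depending only on Baseline, the expected later score is μ_post + ρ(y₀ − μ₀). Among the retained, therefore:

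- error in the post-Baseline level = −ρδ
- error in the change = +(1 − ρ)δ, which is toward zero when the true change is negative.

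**Results under the 11.3 rule** (g from averaging the loss curve over the assumed Baseline distribution):

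| Slope | p | g | δ | Change, ρ=0.4 | Change, ρ=0.6 | Level error, ρ=0.4 | Level error, ρ=0.6 |
|---|---|---|---|---|---|---|---|
| 0.2 | 10% | 1.22 | 0.12 | -0.93 | -0.95 | -0.05 | -0.07 |
| 0.2 | 20% | 1.20 | 0.24 | -0.86 | -0.90 | -0.10 | -0.14 |
| 0.2 | 30% | 1.19 | 0.36 | -0.79 | -0.86 | -0.14 | -0.21 |
| 0.4 | 10% | 2.27 | 0.23 | -0.86 | -0.91 | -0.09 | -0.14 |
| 0.4 | 20% | 2.17 | 0.43 | -0.74 | -0.83 | -0.17 | -0.26 |
| 0.4 | 30% | 2.11 | 0.63 | -0.62 | -0.75 | -0.25 | -0.38 |

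For example, in the last row at ρ = 0.4 the change is -1.0 + 0.6 × 0.63 = -0.62, or 38% too small. With everyone kept and Baseline as a response, the change is about -1.0.

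**Second check under other assumptions.** Large-sample simulation with 200,000 subjects per setting, SD 2.5, Baseline mean 6.0, Final mean 4.5 (true change -1.50), intraclass correlation 0.3 to 0.7 and the same loss fractions:

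| Loss mechanism | Change, all kept | Change, 11.3 rule | Final mean, all kept | Final mean, 11.3 rule |
|---|---|---|---|---|
| Depends on Baseline score | -1.49 to -1.51 | -1.06 to -1.42 | 4.49 to 4.51 | 4.06 to 4.44 |
| Completely at random | about -1.50 | about -1.50 | about 4.50 | about 4.50 |
| Depends on the unseen first post-Baseline score | -1.54 to -1.66 | -1.49 to -1.51 | 4.34 to 4.46 | 4.05 to 4.44 |

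The formula agrees. At correlation 0.3 and 30% loss, δ = 6.00 − 5.37 = 0.63, so the change is -1.50 + 0.7 × 0.63 = -1.06 and the Final mean is 4.50 − 0.3 × 0.63 = 4.31, both as simulated.

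**Baseline as covariate only.** With post-Baseline scores alone as the response (65 subjects, 13 without any), fitting with and without those 13 gave identical estimates (difference 0.0), because they contribute no rows.

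**The case against.** The strongest objection is that the bias needs a model the plan has not fixed. Section 2.1.2 speaks of scores at visits after Baseline, and 11.4.5 adjusts for baseline characteristics. If the Baseline score is only a covariate, the restriction changes nothing. This stands as a condition. It does not dispose of the point: 11.4.5 names no Baseline symptom score as a covariate, Section 2.2.2 includes Baseline scores in the endpoint, and a single-arm model with time as its effect of interest cannot show change from Baseline unless Baseline is an outcome row.

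Second, admitting everyone is not always better. If loss depends on unseen scores, the all-subjects estimate slightly overstates the change (-1.54 to -1.66 against -1.50), while the restricted set gets the change nearly right. Both sets put the Final mean too low, the restricted set more so. This stands and is why both should be reported.

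Third, the size is assumed and modest. With the first set of inputs the standard error of the change to the mean of four visits is √(6.25 × (1 − ρ) × 1.25 / 65), or 0.27 at ρ = 0.4 and 0.22 at ρ = 0.6. The 20%-loss bias of 0.10 to 0.26 is at most about one standard error.

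A reader might also infer that the symptom trend would describe only subjects well enough to return. The documents do not support that. Visits may be virtual or by phone, PHQ9 may be electronic, and one score at any of four visits keeps a subject in. The coded reasons for missing scores include inconvenience, privacy, language and administrative failure. ESAS is specified for clinic or virtual visits, so a phone visit may lack it for reasons unrelated to illness.

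**Conclusion.** The point holds conditionally. Section 11.3 discards collected Baseline scores that the planned type of model can use. With Baseline as an outcome row and loss dependent on the Baseline score, the change is about 5% to 38% too small and the post-Baseline level about 0.05 to 0.4 points too low, under the assumed SD, correlation, loss fraction and loss slope. None of these inputs is in the documents.

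A reader might conclude that the population rule alone causes the error and that the planned model would remove it. That goes too far: the role of Baseline is unspecified, the change is unbiased either way if loss is completely at random, and neither set is free of bias if loss depends on unseen scores. Nor does the calculation show bias in the matched comparison. It covers only the single-arm trend, and no corresponding post-Baseline rule is stated for the controls. This is a worthwhile correction to a secondary analysis.

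**What to change.** - **Section 11.3:** define the mixed-model population as all evaluable subjects with at least one valid score for the symptom being modelled, Baseline included. Specifying the symptom also settles whether a post-Baseline PHQ9 alone admits a subject to the pain model, which the present and/or leaves open.
- **Section 11.4.5:** state that the Baseline study-visit score is an outcome row and that time is a factor.
- **First-visit ESAS:** do not enter it as an outcome row. It is the eligibility screen and a matching variable, so as a response it would build regression to the mean into the time effect. Its use in matching already gives it a role in the analysis, as Table 2 requires.
- **Present restricted set:** keep it for the average post-Baseline comparison, which needs it, and use it as a sensitivity analysis for the mixed models. Report how many subjects it excludes, with their Baseline scores and the reasons recorded under Section 5.1.3.

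The cost is a few sentences in two sections and one extra model fit per symptom, with no new data, visits or patients. The small downside is that the all-subjects estimate may slightly overstate the change if loss depends on unseen scores, which reporting both results makes visible.
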